3.1 General Design

This will be a pragmatic, single-center, cross-over pilot study to evaluate the safety and efficacy of UDCA in patients subjects with hepatic sarcoidosis. For this project, potential subjects (i.e. patients with a prior diagnosis of sarcoidosis and lab/imaging findings suggestive of hepatic sarcoid) seen at Penn Medicine clinics will be identified by the study team and screened in the Hepatology clinic at the Perelman Center for Advanced Medicine. . At least ten patients will be enrolled for an expected twelve month duration. Frequency of clinical evaluations will align with standard of care monitoring of this patient population; the study-specific intervention will be the administration of UDCA (unblinded). Study-specific procedures include research labs, patient-reported outcomes questionnaires; optional biomarker retains, methacetin breath test (MBT) measurements; further details on the schedule of events for this study can be found in section 6.

NOTE: All subjects enrolled under Amendment 10 (JUN 2021) or later will NOT be included in the optional MBT sub-study.

3.1.1 Screening Visit

At the screening visit, prior to any study-related screening procedures being performed on the subject, the informed consent statement will be reviewed with the subject by the PI and signed and dated by the subject and the PI. For all subjects, the PI and/or study coordinator will: record medical history, record prior and current medications, record general health (including averse events and illnesses), conduct physical examination (including assessment of certain physical symptoms that are associated with liver disease), collect vital signs, perform a Fibroscan (ultrasound of abdomen to measure liver stiffness), administer quality of life (QoL) questionnaires, and collect blood samples for routine laboratory tests specific to liver function. A urine pregnancy test will be performed at screening for women of child-bearing potential (WOCBP). These subjects will also be required to confirm the use of appropriate contraceptive prior to receiving UDCA while in the study.

3.1.2 Study Observational Phase

Once the PI confirms a subject's eligibility, subject will be called by the study coordinator and asked to come back to the clinic for 4 future visits over the course of 1 year. The visits will occur approximately every 3 months, according to standard of care monitoring of this patient population.

The Day 1 and Month 3 study assessments will be observational in nature, and can be performed remotely, per standard of care for patients with hepatic sarcoidosis. During the Day 1 telephone encounter, the study coordinator will review current medications with subjects. During the Month 3 visit, for all subjects, the PI and/or coordinator will: review prior and current medications, record your general health (including adverse events and illnesses), conduct physical examination, including assessment of certain physical symptoms that are associated with liver disease, collect vital signs (if visit is conducted in clinic), height and weight, and collect blood samples for routine laboratory tests specific to liver function. If visiting the clinic at Month 3 is impractical for the subject for any reason, Month 3 assessments can be conducted remotely.

3.1.3 Study Intervention Phase

Study medication will be dispensed at Month 6 to initiate the interventional phase of the study. During study visits, for all subjects, the research team will: review prior and current medications, record your general health (including adverse events and illnesses), conduct physical examination, including assessment of certain physical symptoms that are associated with liver disease, collect vital signs, height and weight, perform a Fibroscan (ultrasound of abdomen to measure liver stiffness), perform MBT (Month 6 and Month 12), administer QoL questionnaires, collect blood samples for routine laboratory tests specific to liver function, initiation of study medication (Month 6), and assess medication compliance (Month 9 and Month 12). For WOCBP, urine pregnancy testing will be performed at Month 6 and every 4 weeks while on drug. Home pregnancy testing kits will be provided for this. WOCBP will be contacted by the study coordinator every 4 weeks while on drug for reporting results of urine pregnancy tests. Subjects will be instructed to notify [name] or the study coordinator if they become pregnant at any time during the study, and to discontinue study drug immediately upon suspecting pregnancy. Drug will be discontinued immediately for any subject who becomes pregnant during the study. Pregnancy will not be considered an AE, nor will an elective abortion to terminate a pregnancy without medical reasons. Pregnancy outcomes will not be followed for this study.

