1.2.1.2 Clinical Studies in Adults: Pregnancy Category B

Teratology studies have been performed in pregnant rats at oral doses up to 2,000 mg/kg/day (12,000

mg/m²/day, 22 times the recommended maximum human dose based on body surface area) and in pregnant rabbits at oral doses up to 300 mg/kg/day (3,600 mg/m²/day, 7 times the recommended maximum human dose based on body surface area) and have revealed no evidence of impaired fertility or harm to the fetus due to UDCA.

There are no adequate or well-controlled studies in pregnant women. Because animal reproduction studies are not always predictive of human response, this drug should be used during pregnancy only if clearly needed. It is also not known whether UDCA is excreted in human milk. Because many drugs are excreted in human milk, caution should be exercised when URSO 250® and URSO Forte® are administered to a nursing mother.

There are no contraceptive requirements for males. Ursodiol was not genotoxic in the Ames test, the mouse lymphoma cell (L5178Y, TK+/-) forward mutation test, the human lymphocyte sister chromatid exchange test, the mouse spermatogonia chromosome aberration test, the Chinese hamster micronucleus test and the Chinese hamster bone marrow cell chromosome aberration test. Ursodiol at oral doses of up to 2,700 mg/kg/day (16,200 mg/m²/day, 29 times the recommended maximum human dose based on body surface area) was found to have no effect on fertility and reproductive performance of male and female rats.

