7.4.3 Safety Analysis

See 7.2.

7.5 **Subject Population(s) for Analysis**

All-treated population: Any subjects enrolled into the study that received at least one dose of investigational product.

8 **Safety and Adverse Events**

8.1 **Definitions**

8.1.1 **Adverse Event**

An **adverse event** (AE) is any symptom, sign, illness or experience that develops or worsens in severity during the course of the study. Intercurrent illnesses or injuries should be regarded as adverse events. Abnormal results of diagnostic procedures are considered to be adverse events if the abnormality:

- results in study withdrawal
- is associated with a serious adverse event
- is associated with clinical signs or symptoms
- leads to additional treatment or to further diagnostic tests
- is considered by the investigator to be of clinical significance

For FDA regulated studies the FDA defines an adverse event as the following:

Adverse event means any untoward medical occurrence associated with the use of a drug in humans whether or not considered drug related.

Adverse events will be collected at each study visit. The start and stop date(s) of the event(s) (if known), and relationship to study drug (UDCA), to methacetin or, MBT procedure will also be collected.

Anticipated AEs related to the study drug are listed in the package insert for UDCA/ursodiol. There are no anticipated AEs with methacetin.

8.1.2 **Serious Adverse Event**

Adverse events are classified as serious or non-serious. A **serious adverse event** is any AE that is:

- fatal
- life-threatening
- requires or prolongs hospital stay
- results in persistent or significant disability or incapacity
- a congenital anomaly or birth defect
- an important medical event

Important medical events are those that may not be immediately life threatening, but are clearly of major clinical significance. They may jeopardize the subject, and may require intervention to prevent one of the other serious outcomes noted above. For example, drug overdose or abuse, a seizure that did not result in in-patient hospitalization, or intensive treatment of bronchospasm in an emergency department would typically be considered serious.

All adverse events that do not meet any of the criteria for serious should be regarded as **non-serious adverse events**.

8.2 **Recording of Adverse Events**

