At each contact with the subject, the investigator will seek information on adverse events by specific questioning and, as appropriate, by examination. Information on all adverse events will be recorded immediately in the source document, and also in the appropriate adverse event module of the case report form (CRF). All clearly related signs, symptoms, and abnormal diagnostic procedures results should be recorded in the source document, though should be grouped under one diagnosis.

All adverse events occurring during the study period will be recorded. The clinical course of each event will be followed until resolution, stabilization, or until it has been determined that the study intervention or participation is not the cause. Serious adverse events that are still ongoing at the end of the study period will be followed up to determine the final outcome. Any serious adverse event that occurs after the study period and is considered to be possibly related to the study intervention or study participation will be recorded and reported immediately.

All subjects taking part in the optional MBT substudy will be monitored for AEs for 24 hours following MBT administration. This assessment will be conducted remotely; subjects will be contacted by phone one day following MBT administration.

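### Outcomes of UDCA-exposed pregnancies are not systematically ascertained, although a birth defect is a listed serious adverse event

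*Combined protocol and SAP*

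**What the plan says.** Section 3.1.3 sets up active detection of pregnancy on treatment. For women of child-bearing potential, "urine pregnancy testing will be performed at Month 6 and every 4 weeks while on drug", with a coordinator contact every four weeks to collect the result. Subjects are told to notify the team of any pregnancy, and the drug is stopped. The section then says "Pregnancy will not be considered an AE, nor will an elective abortion to terminate a pregnancy without medical reasons", and closes with "Pregnancy outcomes will not be followed for this study".

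The safety sections are written in general terms. Section 8.1.2 includes "a congenital anomaly or birth defect" among the criteria that make an adverse event (AE) serious. Section 8.2 has two follow-up rules:

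- For events open at the end: "Serious adverse events that are still ongoing at the end of the study period will be followed up to determine the final outcome".
- For later events: "Any serious adverse event that occurs after the study period and is considered to be possibly related to the study intervention" or to study participation "will be recorded and reported immediately".

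On prior knowledge, section 1.2.1.2 says "There are no adequate or well-controlled studies in pregnant women". It also reports rat and rabbit studies that showed no fetal harm.

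**The concern.** The plan takes trouble to find the exposure and then declines to learn its result. Section 8.2 has AEs followed until they resolve or stabilise, but pregnancy is defined as not being an AE, so that rule does not carry the team through to the birth. No other section provides a route to the birth outcome. One SAE category that the protocol itself names therefore has no planned means of ascertainment.

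Section 3.1.3 is also awkward on its own terms. It excludes from AE status only an elective termination without medical reasons. That implies a spontaneous loss or a medically indicated termination may count as an AE, and telling these apart requires the outcome that the next sentence says will not be followed.

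What is at stake is safety information. Safety is a secondary objective and endpoint (sections 2.2 and 3.2.2), and the protocol describes the human pregnancy data as inadequate. No efficacy endpoint is involved.

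**Working it through.** The plan gives no figure to reproduce. The check has three parts.

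**1. The rules side by side.**

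| Step | Rule | Section |
|---|---|---|
| Pregnancy is detected | Test at Month 6 and every 4 weeks on drug; subject notifies the team | 3.1.3 |
| Pregnancy is classified | Not an AE | 3.1.3 |
| Outcome is sought | No | 3.1.3 |
| Birth defect is classified | Serious | 8.1.2 |
| Possibly related SAE after the study | Recorded and reported immediately | 8.2 |

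The last two rows apply only once a birth defect is known. The third row removes the planned way of knowing. The relatedness condition in section 8.2 narrows the duty but does not close the gap, because relatedness cannot be judged for an outcome that nobody has learned.

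**2. Timing.** Inputs: drug is taken from Month 6 to Month 12 (sections 3.1.3 and 5); core participation is 12 months and the further 12 months are optional (section 4.3); AE assessment is scheduled at Months 18 and 24 (section 6). A term of 9 months is my assumption.

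- Earliest on-drug conception: Month 6 + 9 = Month 15.
- Latest on-drug conception: Month 12 + 9 = Month 21.

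Every term birth therefore falls after Month 12. A birth at Months 15-18 precedes the Month 18 visit, and one at Months 18-21 precedes the Month 24 visit. AE questioning at those visits could reveal a defect, but only in subjects who accept the optional follow-up. For the others, no contact is scheduled after the birth.

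**3. Expected number of exposed pregnancies.** Inputs: N = 40 (target) or 10 (minimum), from the Study Summary. Two inputs are assumptions that the documents do not supply: the share of subjects of child-bearing potential, p = 0.30 to 0.50, and the annual probability of conception with contraception, r = 0.02 to 0.08. Exposure is half a year.

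Expected pregnancies = N × p × (1 − (1 − r)^0.5)

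- Six-month probability at r = 0.02: 1 − 0.98^0.5 = 0.01005.
- Six-month probability at r = 0.08: 1 − 0.92^0.5 = 0.04083.

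| N | Low: p = 0.30, r = 0.02 | High: p = 0.50, r = 0.08 |
|---|---|---|
| 40 | 12 × 0.01005 = 0.12 | 20 × 0.04083 = 0.82 |
| 10 | 3 × 0.01005 = 0.03 | 5 × 0.04083 = 0.20 |

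These are counts of pregnancies, not of birth defects. The expected number of missed SAEs is smaller and is not estimated here.

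**The case against.** The strongest reply is that the rules can all be obeyed together. Section 8.1.2 classifies events and section 8.2 says what to do with an event once it is known and judged possibly related. Neither orders an active search for birth outcomes. Section 3.1.3 can be read as the specific ascertainment rule: no scheduled outcome follow-up, but a defect that becomes known is handled as an SAE. This stands. A reader might infer that the sections flatly contradict each other, and the text does not support that.

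A reader might also infer that a birth defect could not be detected at all. That goes too far. The team will know of the pregnancy, the subject may report spontaneously, section 8.2 requires AE questioning at each contact, the schedule marks AE assessment at Months 18 and 24, and section 6.7.1 allows safety events to be followed up after withdrawal. Nor is every later birth defect reportable under section 8.2, which covers only SAEs considered possibly related to the intervention or to participation.

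Mitigation is real as well. Women who are pregnant or planning pregnancy are excluded (section 4.1), contraception is confirmed before UDCA (section 3.1.1), the drug is stopped on pregnancy, and the animal data in section 1.2.1.2 are reassuring.

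Finally, section 4.5 says that pregnant women, fetuses and neonates are not part of the research, so collecting a neonatal outcome needs a word of explanation there. This also stands and is taken up in the fix.

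None of this supplies a planned route to the outcome for a subject who declines optional follow-up. Rarity limits the practical weight of the gap, but it equally limits the cost of closing it.

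**Conclusion.** The point holds as a gap in safety ascertainment. After a known on-drug exposure, the plan leaves a listed SAE category to spontaneous report or optional visits. The timing result rests on a 9-month term. The size, about 0.1-0.8 exposed pregnancies at 40 subjects and 0.03-0.2 at 10, rests on the assumed child-bearing share and conception rate. It covers only the six months of study drug, not UDCA continued by prescription afterwards. The correction is cheap and worth making. It has no bearing on the validity of the trial or on the ALP and GGT analysis.

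**What to change.** Reconcile sections 3.1.3, 8.1.2 and 8.2:

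- **Section 3.1.3:** replace the sentence on outcomes with a statement that, for any pregnancy with UDCA exposure and with the subject's permission, the outcome will be ascertained by one contact after the expected delivery date.
- **Sections 8.1.2 and 8.2:** add a cross-reference so that any congenital anomaly found this way is handled under the existing SAE rules, including the relatedness judgement.
- **Section 4.5:** state that this contact is safety reporting and does not enrol pregnant women or neonates.
- **Consent form:** add a line asking permission for the contact.

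The cost is these text changes and, at the numbers above, probably zero or one extra contact over the whole study. Dosing, contraception and discontinuation rules are untouched.

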3.1.4 Follow Up Phase (Optional)

Subjects will have the option to remain on UDCA after study completion if it can be obtained through prescription outside of the trial. PI will continue to follow all of these patients in hepatology clinic after completion of the trial as clinically indicated. Data will be collected for an additional 12 months.

3.2 Study Endpoints

3.2.1 Primary Study Endpoints

To evaluate the efficacy of UDCA in improving liver function, the following laboratory parameters will be assessed:

1. Reduction in ALP and/or GGT from baseline

3.2.2 Secondary Study Endpoints

1. safety and tolerability of UDCA in patients with hepatic sarcoidosis (liver function tests will be monitored alongside reporting of adverse events)
2. efficacy of UDCA in the improvement of liver stiffness as a clinical parameter of liver function (Fibroscan stiffness readings (in kPa) will be monitored)
3. Changes in quality of life parameters prior to and following intervention with UDCA (PRO questionnaire scores will be assessed for improvements)
4. Changes in the ¹³C-methacetin breath tests in all subjects prior to and following intervention with UDCA (exploratory endpoint)
5. Changes in ACE and sIL2R

4 Study Population and Duration of Participation

A minimum of ten adult patients with a prior diagnosis of sarcoidosis and lab/imaging findings suggestive of hepatic sarcoid will be enrolled for a twelve-month comprehensive observational and interventional period. Subjects will have the option to continue being followed for another year; thus the study will last approximately 24 months, cumulative of recruitment, enrollment, data collection, and analysis.

4.1 Eligibility Criteria

Study Eligibility Criteria	
Inclusion	Exclusion
1. Male or female, at least 18 years of age, and able to provide written informed consent 2. Systemic sarcoidosis with evidence of liver involvement as denoted by any of the following: - Elevated liver-specific alkaline phosphatase - Granulomas on liver biopsy - Hepatomegaly on imaging - Portal Hypertension (via imaging or endoscopy) OR granulomas on liver biopsy (not attributable to infection) AND elevated liver-specific alkaline phosphatase 3. Stable dose of immunosuppressant \geq 6 months (with the exception of changes in prednisone less than or equal to 20 mg or prednisone equivalent) 4. If cirrhotic, absence of hepatocellular carcinoma as indicated by imaging within 6 months of screening	1. Female who is pregnant, planning to become pregnant during the study, or breastfeeding 2. Clinically significant abnormalities, co-morbidities, or recent alcohol/drug abuse that make the subject an unsuitable candidate 3. hepatitis B, hepatitis C, alcohol-related liver disease, autoimmune hepatitis, primary biliary cholangitis, primary sclerosing cholangitis) 4. Currently on or prior intolerance to UDCA 5. Receipt of any investigational product within a time period equal to 10 half-lives of the product, or 6 weeks (whichever is longer), to study drug administration 6. Current evidence of hepatic decompensation (variceal bleeding, hepatic encephalopathy, or ascites). In the event potential participant is post-transplant, no evidence of hepatic decompensation since transplantation

4.2 Subject Recruitment

Potential subjects will be recruited from Penn Medicine clinics as well as remote clinics. The PI and study team will identify study candidates; referrals from physicians or the subjects themselves will be accepted and further assessed for eligibility by the PI during a screening visit which will take place in the Hepatology clinic at the Perelman Center for Advanced Medicine.

4.3 Duration of Study Participation

The expected duration of the subjects' participation is initially 12 months. Monitoring for an additional 12 months will be optional.

4.4 Total Number of Subjects and Sites

It is approximated that 15 subjects will need to be screened in order to produce 10 evaluable subjects.

4.5 Vulnerable Populations:

All subjects to be recruited in this trial will be referred to us by their physician. Children, pregnant women, fetuses, neonates, or prisoners are not included in this research study. No mentally disabled or economically disadvantaged persons will be enrolled. Only subjects able to provide informed consent autonomously will be eligible for enrollment. Penn students or employees will not be directly targeted or excluded. In the event that Penn students or employees present for screening, they will be informed that their decision regarding whether or not to participate will in no way impact their standing at the University.

5 Study Intervention (UDCA)

During the second 6 months of the study, all subjects will receive open-label UDCA 250mg or 500mg tablets, or 300mg capsules. This will be obtained through prescription and initiated at the Month 6 visit. Subjects will take this medication twice daily as instructed for 6 months, as described above. If the subject is taking a sequestrant, the UDCA would need to be taken 5 hours apart from it (because bile acid sequestrants, such as cholestyramine, can bind UDCA). Bile acid sequestrants and estrogen can lower

the therapeutic effect of UDCA, but these are not contraindications to taking UDCA. More information on the study medication, UDCA, can be found in section 1.2 as well as the package insert for Ursodiol.

5.1 Description

See section 1.2 and 1.3, as well as the package inserts for Ursodiol for more information.

5.2 Intervention Regimen

Dosing for study participants with mild liver disease:

After at least 3 months of treatment and if subject weighs more than 200 lbs., PI may decide to increase dose of study drug based on a review of lab results and ability to tolerate the study drug. Dose would be increased to two tablets (500mg) with breakfast and one tablet (250mg) with dinner. If subject is on the 300mg option, their dosage would be calculated accordingly using these models.

Dosing for study participants with moderate liver disease:

If during the screening period of the study, it is determined that subject has moderate liver disease, subject may receive corticosteroids (per standard of care). If subject is already taking corticosteroids, dose may be increased.

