1.3 Dose Rationale

The recommended adult dosage for URSO 250® and URSO Forte® in the treatment of PBC is 13-15 mg/kg/day administered in two to four divided doses with food. The URSO Forte® scored tablet can be broken in halves to provide recommended dosage. Due to the bitter taste, segments should be stored separately. Half-tablets (scored URSO Forte® 500 mg tablets broken in half) maintain acceptable quality for up to 28 days when stored in the current packaging (bottles) at 25°C (77°F). The recommended adult dosage for Actigall 300mg (for treatment of radiolucent gallbladder stones) is 8-10 mg/kg/day given in 2-3 divided doses. Dosing regimen should be adjusted according to each patient's need at the discretion of the physician. We will be using 250mg or 500mg tablets, or 300mg capsules for this protocol. This decision will be determined based on price, pill burden, and adherence complexity. Subjects will receive a targeted dose of 13-15 mg/kg/day in divided doses to be taken with meals. As the approach to the treatment of hepatic sarcoid in this protocol is designed to resemble that of the treatment of PBC, the targeted dose for subjects taking the Actigall 300mg capsules will also be 13-15 mg/kg/day, which remains within safe means of dosing for this formulation. For subjects in which the dosing increment does not fall into the 13-15mg/kg range, we will initiate intervention using the lower dose. For example, if a subject is 80kg, the dose range is from 1040-1200mg/kg/day. We will initiate 1000mg/day (12.5mg/kg/day in our 80kg example) rather than 1250mg/day (15.6 mg/kg/day). If the subject tolerates this lower dose well and the ALP and GGT have not reached a 20% decrease by month 9 (after 3 months of treatment), the subject will receive an additional 250mg tablet for daily administration. A dose calculation assessment will be performed at each in-person visit following UDCA administration. UDCA doses in the range of 17-23mg/kg have been used in long-term trials for PSC (PMID: 11606503, PMID:16285948). The UDCA studies in PSC demonstrated an improvement in ALP and GGT in subjects taking UDCA without an increase in adverse events from the medication.

Accidental or intentional overdose with UDCA has not been reported. The most severe manifestation of overdose would likely consist of diarrhea which should be treated symptomatically.

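### The fixed dose 'increase' in section 5.2 for subjects over 200 lb conflicts with the weight-based dose in section 1.3 and is usually no increase

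*Combined protocol and SAP*

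**What the plan says.** Section 1.3 sets the dose by weight: "Subjects will receive a targeted dose of 13-15 mg/kg/day in divided doses to be taken with meals". Capsule users have the same target: "the targeted dose for subjects taking the Actigall 300mg capsules will also be 13-15 mg/kg/day". Where no whole number of units fits the range, the rule is: "For subjects in which the dosing increment does not fall into the 13-15mg/kg range, we will initiate intervention using the lower dose". The worked example is an 80 kg subject, who starts on 1000 mg rather than 1250 mg. If a subject started on such a lower dose tolerates it, and ALP and GGT have not fallen by 20% by Month 9, "the subject will receive an additional 250mg tablet for daily administration". Section 1.3 also leaves room for physician adjustment and adds a recurring check: "A dose calculation assessment will be performed at each in-person visit following UDCA administration".

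Section 5.2, under mild liver disease, adds a separate rule: "After at least 3 months of treatment and if subject weighs more than 200 lbs., PI may decide to increase dose of study drug", on the basis of laboratory results and tolerability. The amount follows: "Dose would be increased to two tablets (500mg) with breakfast and one tablet (250mg) with dinner". For capsules it says only: "If subject is on the 300mg option, their dosage would be calculated accordingly using these models". Section 5.2 does not give the dose from which this is an increase, and does not say how the rule relates to the Month 9 step in section 1.3.

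**The concern.** A fixed regimen is an increase only if it exceeds what the subject already takes. Subjects over 200 lb have the highest weight-based doses in the study, yet the regimen in section 5.2 is small. If it does not exceed the section 1.3 start, the instruction contradicts its own purpose. A prescriber is left to choose between leaving the dose alone, lowering it, or working out an amount that the protocol does not state.

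At stake is the dose given to heavier subjects in the last three months of a six-month treatment period, in a pilot whose effect size is meant to inform a later powered study.

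**Working it through.** **Inputs.** Target 13-15 mg/kg/day, round-down rule and available units (250 mg and scored 500 mg tablets, 300 mg capsules): section 1.3. Threshold of 200 lb and the fixed regimen: section 5.2. Conversion: 200 × 0.45359 = 90.72 kg.

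**The plan's own example.** At 80 kg, 13 × 80 = 1040 and 15 × 80 = 1200 mg. No multiple of 250 lies between them, so the start is 1000 mg (1000/80 = 12.5 mg/kg); 1250 mg would be 15.6 mg/kg. This matches section 1.3.

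**Target at the threshold.** 13 × 90.72 = 1179 mg; 15 × 90.72 = 1361 mg.

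**Section 1.3 start over 200 lb.** Take the lowest multiple of the unit within 13-15 mg/kg; if there is none, take the next lower multiple. A higher unit becomes available when it equals 15 mg/kg: 1500/15 = 100 kg, 1750/15 = 116.7 kg, 1800/15 = 120 kg, 2000/15 = 133.3 kg.

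| Weight (kg) | 250 mg steps | Whole 500 mg tablets | 300 mg capsules |
|---|---|---|---|
| 90.7 to <100 | 1250 | 1000 | 1200 |
| 100 to <116.7 | 1500 | 1500 | 1500 |
| 116.7 to <120 | 1750 | 1500 | 1500 |
| 120 to <133.3 | 1750 | 1500 | 1800 |
| 133.3 and over | 1750 or more | 2000 or more | 1800 or more |

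**Reading (a): three 250 mg tablets.** 3 × 250 = 750 mg/day, and 750/90.72 = 8.3 mg/kg at the threshold, lower above it. The smallest starts in the table are 1250, 1000 and 1200 mg, so 750 mg is below all of them. Against the smallest tablet starts, 750/1250 = 0.60 (40% lower) and 750/1000 = 0.75 (25% lower). 750 mg would meet the target only between 750/15 = 50 kg and 750/13 = 57.7 kg.

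**Reading (b): two 500 mg tablets plus one 250 mg tablet.** 2 × 500 + 250 = 1250 mg/day.
- Below 100 kg, 250 mg steps: 1250 − 1250 = 0.
- Below 100 kg, whole 500 mg tablets: 1250 − 1000 = +250 mg, the same size as the section 1.3 step.
- From 100 kg, any formulation: 1250 − 1500 = −250 mg, or a larger reduction.

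**Capsules.** 1250/300 = 4.17, so reading (b) cannot be made from capsules. Four capsules are the 1200 mg start; five are 1500 mg. The text does not choose.

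**Example at 105 kg (231 lb).** 13 × 105 = 1365 and 15 × 105 = 1575, so the start is 1500 mg (14.3 mg/kg) on any formulation. Section 5.2 gives 750 mg (7.1 mg/kg) or 1250 mg (11.9 mg/kg).

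**Where both rules can apply.** The section 1.3 step is for rounded-down subjects. In 250 mg steps, rounding down begins at 1250/13 = 96.2 kg and ends at 100 kg, and again runs from 1500/13 = 115.4 to 116.7 kg. At 98 kg, section 1.3 would give 1250 + 250 = 1500 mg, while section 5.2 gives 750 or 1250 mg.

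**The case against.** The strongest reply is that section 5.2 is coherent in one case. Section 1.3 leaves the formulation open. On whole 500 mg tablets between 90.7 and 100 kg, reading (b) is exactly one 250 mg step above the start. That stands, but it covers one formulation and one weight band. The 80 kg example, the scored 500 mg tablet and the 250 mg Month 9 step all show that the protocol also works in 250 mg steps.

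A second reply is that context protects subjects. The increase is optional, section 1.3 allows physician judgement, section 5.1 refers back to sections 1.2 and 1.3, and the dose is rechecked at in-person visits. A clinician told to increase would hardly write 750 mg for someone already on 1250 mg. This limits the harm, but it does not correct the stated amount. The recheck is tied to in-person visits, and the schedule in section 6 allows Month 9 to be a phone call, although section 5.3 expects a return to the clinic.

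Three stronger readings are tempting and are not supported:
- A reader might infer that following section 5.2 literally always lowers the dose. Under reading (b) below 100 kg the dose is unchanged or rises by 250 mg.
- A reader might infer that capsule users would get two capsules plus one, 900 mg/day. No such dose is stated, and section 1.3 keeps capsule users at the 13-15 mg/kg target. The fair criticism is that the amount is undefined.
- A reader might call this a failed calculation. Section 5.2 states no total, and the one worked figure, in section 1.3, reproduces. The fault is a conflict between two sections.

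**Conclusion.** The point holds as a minor correction. In 250 mg steps, neither reading of the fixed regimen exceeds the section 1.3 start at any weight over 200 lb. From 100 kg both readings are reductions on every formulation. The only real increase is 250 mg, on whole 500 mg tablets below 100 kg, under reading (b). The documents do not show which total was intended.

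The result assumes that the subject is on the section 1.3 dose for the current weight. Where two multiples fit the range the lower was used; choosing the higher would only widen the shortfall.

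The consequence is limited. Escalation is at the PI's discretion, it can affect only Months 9 to 12 of the main study, and the documents give no weight distribution, so the number of subjects is unknown. A reader might infer that the pilot's effect size would be materially distorted; nothing in the documents allows that to be sized, and no sample size or power figure depends on this dose.

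**What to change.** In section 5.2, keep the trigger (at least three months, over 200 lb, laboratory review, tolerability). Delete the fixed-regimen and capsule sentences and put in their place:

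*The current daily dose may be increased once, by one 250 mg tablet (one 300 mg capsule for capsule users). Where the section 1.3 Month 9 step applies, that step governs and no further 5.2 increase is given.*

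In section 1.3, after the mention of the extra 250 mg tablet, add: *(or one 300 mg capsule for capsule users)*. Without this, a capsule user who qualifies for the Month 9 step would be told to add a tablet of a different strength.

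One such step above the section 1.3 start, over 200 lb, reaches at most (1500 + 250)/100 = 17.5 mg/kg/day with a tablet and (1500 + 300)/100 = 18.0 mg/kg/day with a capsule. Both are above the 13-15 mg/kg target. Section 1.3 mentions experience at 16-20 mg/kg (seven patients) and 17-23 mg/kg (trials in PSC). Whether to add a mg/kg ceiling is a clinical choice for the investigators and is not part of the required change.

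Cost: a protocol amendment that replaces two sentences in section 5.2 and adds one parenthesis in section 1.3. No new data or visits are needed.
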